13.1.3 Supportive Analyses

No supportive analyses are planned for primary efficacy endpoint.

13.2 Key Secondary Efficacy Endpoints

Patient Global Impression of Change (PGIC) at Week 4 with reference to baseline status

The PGIC will be summarized as both a categorical and continuous variable (including 95% CI for the mean) at every study visit week. This endpoint will be analyzed using analysis of variance (ANOVA) with treatment, sex, and baseline K-L score as factors on LOCF data. The comparison at week 4 will be viewed as key secondary.

The proportion of patients with PGIC scores of “very much improved” and “much improved” will also be summarized and compared between treatments using a logistic regression with treatment, sex and baseline K-L score as factors. Additionally, this proportion will be compared using a Cochran-Mantel-Haenzel test stratified by baseline K-L score and sex.

Change from Baseline to Week 4 in Western Ontario and McMaster Universities

Osteoarthritis Index (WOMAC) total score

The change from baseline in the WOMAC Index total score will be analyzed using analysis of covariance (ANCOVA) with baseline WOMAC score as covariate, treatment, sex, and baseline K-L score as main effects on LOCF data.

Proportion of subjects who are responders as defined by 30% and 50% reduction from Baseline to Week 4 in the average of the daily average NRS pain intensity scores will be evaluated by the Cochran-Mantel-Haenszel (CMH) General Association Test, missing data considered as “non-respond”, controlling for baseline K-L score and sex.

13.3 Secondary Efficacy Endpoints

Change from Baseline to every study week visit in:

Weekly average of the daily worst NRS pain intensity scores will be evaluated using ANCOVA with baseline SF-12 score as covariate, treatment, baseline K-L score and sex as main effects on LOCF data.

Brief Pain Inventory–Short Form (BPI-sf) will be evaluated using ANCOVA with baseline SF-12 score as covariate, treatment, baseline K-L score and sex as main effects on LOCF data.

12-item Short Form Survey (SF-12) The change from baseline to week 4 will be evaluated using ANCOVA with baseline SF-12 score as covariate, treatment, baseline K-L score and sex as main effects on LOCF data.

13.4 Exploratory Efficacy Endpoints

Comparison of average daily rescue medication use

The average daily number of acetaminophen tablets used during the study will be compared between treatments using a Wilcoxon Rank Sum Test stratified by baseline K-L score and sex.

Hospital Anxiety and Depression Scale (HADS) The change from baseline to week 4 will be evaluated using ANCOVA with baseline HADS score as covariate, treatment, baseline K-L score, sex as main effects on LOCF data.

14 SAFETY ANALYSES

All safety analyses will be performed using the actual treatment for the Safety Analysis Set.

14.1 Adverse Events

Adverse events will be coded using MedDRA dictionary, Version 24.0 or newer.

An AE (classified by preferred term) will be considered a treatment-emergent AE (TEAE) if started after first dose administration and no later than last dose date + 30 days. AEs reported on Day -1 based on Baseline (pre-dose) findings (e.g., clinically significantly abnormal vital signs, laboratory test results, or electrocardiogram parameters) will not be considered as TEAEs.

The event counts, the number, and percentage of subjects reporting TEAEs in each treatment group will be tabulated by system organ class (SOC) and preferred term; by SOC, preferred term, and maximum severity; and by SOC, preferred term, and relationship to study drug. If more than one TEAE occurs with the same preferred term for the same subject, then the subject will be counted only once for that preferred term using the most severe and most related occurrence for the summarization by severity and by relationship to study drug. The display in these tables will be sorted alphabetically by SOC and then by descending subject frequency for the preferred terms (counts from ACP-044 treated group) within each SOC.

The event counts, the number and percentage of subjects with any TEAEs will also be tabulated by preferred term without SOCs. This table will be sorted by descending subject frequency within ACP-044 treated group.

The incidence of most frequently reported (preferred terms reported by $\geq 5\%$ of subjects in any treatment group) TEAEs, SAEs reported after treatment start, TEAEs leading to discontinuation of study drug, and TEAEs related to study drug will be summarized by SOC, preferred term, and treatment group. The tables will be sorted alphabetically by SOC and then by descending frequency within each SOC in ACP-044 treated group. In addition, the incidence of fatal treatment-emergent AEs (i.e., events that cause death) will be summarized separately by SOC and preferred term.

The incidence of adverse events of interest, will be summarized separately by SOC and preferred term. The adverse events of interest evaluation will be based on the following prespecified preferred terms of aspartate aminotransferase increased, alanine aminotransferase increased, gamma-glutamyltransferase increased, blood alkaline phosphatase increased, blood bilirubin increased, hyperbilirubinaemia, liver function test increased, blood creatine phosphokinase increased, rash, hypotension, blood pressure decreased, presyncope, hypotension, orthostatic hypotension, pre-syncope, syncope, and bradycardia.

These summary tables except for the most frequently reported TEAEs tables may also be presented for COVID-19 and non-COVID-19 related events, if applicable.

An AE listing by subject will display all events, including those which occur during screening, and will include the verbatim term in addition to the MedDRA SOC and preferred term. This listing will also include all relevant eCRF data associated with the event: date of onset, date resolved, date of last dose, severity, frequency, outcome, relationship to study drug, and action taken with study drug. A listing by subject will display all TEAE, excluding AE that are not treatment-emergent. Separate listings will be presented for subjects with treatment-emergent SAEs, related TEAEs, TEAEs leading to discontinuation, fatal TEAEs (if any), and COVID-19 related TEAEs (if applicable).

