4.5.1 Discontinuation of Study Drug for Individual Subjects

The Investigator and Medical Monitor will review all laboratory, ECG, and related safety data regularly throughout the study for all individual subjects in order to determine whether any individual subject may continue to safely participate in the study. In general, either the Investigator or the Medical Monitor may discontinue the subject from the study at any time when any specific laboratory or ECG data change from Baseline indicates that the subject is placed at increased risk from continued participation in the study.

In rare instances, it may be necessary for a subject to permanently discontinue study drug. Study drug stopping criteria are described below. If a subject experiences any of the below events, it must be documented as an AE.

See [Section 4.5.2](#) for handling of subjects who discontinue and for any further evaluations that need to be completed.

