4.5.1.2 Cardiovascular-Related Stopping Criteria

If a clinically significant finding of orthostatic hypotension, bradycardia, or change in QTcF, as defined below, is identified after enrollment, the Investigator or qualified designee and Medical Monitor will determine if the subject can continue in the study and if any change in subject management is needed.

- Orthostatic hypotension – decrease in systolic blood pressure (SBP) ≥ 20 mmHg or diastolic BP (DBP) ≥ 10 mmHg after transitioning from the supine position (after resting for 5 minutes) to standing at 1 or 3 minutes with or without symptoms such as light headedness or dizziness and not explained by dehydration, illness, or medications
- Significant bradycardia, defined as heart rate of ≤ 45 beats per minute (BPM) on an ECG, or pulse decrease of $\geq 25\%$ from Baseline with resulting heart rate < 60 BPM
- QTcF result > 470 ms for males and > 480 ms for females or QTcF increases ≥ 60 ms from Baseline

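### The adverse-events-of-interest table in SAP 14.1 gives no once-per-subject count across related terms and carries no QT term

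*SAP*

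**What the plan says.** SAP 14.1 defines one table for this purpose: "The incidence of adverse events of interest, will be summarized separately by SOC and preferred term". The terms are fixed in advance. After four liver-enzyme terms (AST, ALT, GGT, alkaline phosphatase) the list continues "blood bilirubin increased, hyperbilirubinaemia, liver function test increased, blood creatine phosphokinase increased, rash, hypotension, blood pressure decreased" and ends "presyncope, hypotension, orthostatic hypotension, pre-syncope, syncope, and bradycardia". Hypotension is entered twice, and presyncope appears in two spellings.

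The counting rule given in the same section, for the severity and relationship tables, works at the level of the term: where a subject has the same preferred term more than once, "then the subject will be counted only once for that preferred term". No rule is given for a subject who has several different but related terms. SAP 14.1 also provides general tables of all TEAEs, including one without body systems: "The event counts, the number and percentage of subjects with any TEAEs will also be tabulated by preferred term without SOCs".

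The protocol promises a summary of TEAEs of special interest (9.5.5) but lists no terms, so the SAP list is the only definition. Protocol 4.5.1.2 groups three cardiovascular findings: "If a clinically significant finding of orthostatic hypotension, bradycardia, or change in QTcF". Protocol 4.5.1.3 names QT prolongation among the adverse events that call for review. Protocol 4.5.1 says of the events in these subsections: "If a subject experiences any of the below events, it must be documented as an AE".

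**The concern.** A table of adverse events of interest should tell the reader how many subjects had each reaction. Here one reaction can be coded under several neighbouring terms: a raised bilirubin under two, a fall in blood pressure under at least two, and a faint or near-faint under two more. Each term has its own row, and one subject may appear in several rows. The rows therefore cannot be added to give the number of subjects, and the largest row may understate it.

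This matters more in a small trial. SAP 1 reports termination with 61 subjects randomized. Most single-term rows are then likely to be 0 or 1, and a cluster of related events in different subjects looks much like one subject with several terms. Safety is assessed descriptively without formal tests (Protocol 9.5.5), so these counts are the analysis.

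The list also covers two of the three cardiovascular findings in Protocol 4.5.1.2 and leaves out the third, QT, without giving a reason.

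**Working it through.** The plan states no figure on this point, so there is none to reproduce.

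**1. Count the list (SAP 14.1).**

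| Group | Entries | Distinct terms |
|---|---|---|
| Hepatic (AST, ALT, GGT, ALP, two bilirubin terms, liver function test) | 7 | 7 |
| Hypotension/syncope (hypotension, orthostatic hypotension, blood pressure decreased, presyncope, syncope) | 7 | 5 |
| CK | 1 | 1 |
| Rash | 1 | 1 |
| Bradycardia | 1 | 1 |
| QT | 0 | 0 |
| Total | 17 | 15 |

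**2. What the rows reveal about subjects.** Let a reaction be split over k terms with row counts r₁ to r_k in an arm of N. The number U of subjects with at least one of the terms satisfies

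max(r_j) ≤ U ≤ min(N, r₁ + … + r_k).

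If every row shows one subject, then 1 ≤ U ≤ k. SAP 1 gives 61 randomized. The split by arm is not given, so equal allocation is assumed: 61/3 = 20.3, about 20 per arm.

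| Group | k | Each row | Lowest U | Highest U |
|---|---|---|---|---|
| Hypotension/syncope | 5 | 1/20 = 5% | 1/20 = 5% | 5/20 = 25% |
| Hepatic | 7 | 1/20 = 5% | 1/20 = 5% | 7/20 = 35% |

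With 21 in an arm the ranges are 4.8% to 23.8% and 4.8% to 33.3%. At the planned 80 per arm they would have been 1.25% to 6.25% and 1.25% to 8.75%. One row per subject turns each range into a single number.

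**3. What the other SAP tables supply.**

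| Finding | Summary from measured values | Combined subject count across related terms or tests |
|---|---|---|
| QTcF | 14.4: subjects above 470 ms (men) or 480 ms (women), and with a rise of 60 ms or more; same thresholds as Protocol 4.5.1.2 | Not needed |
| Orthostatic hypotension | 14.3: protocol definition | None with hypotension or syncope reported as adverse events |
| Bradycardia | 14.3: protocol definition | Not needed |
| ALT, AST, bilirubin, GGT, ALP | 14.2: each analyte on its own | None |
| CK | 14.2: at 3 and 5 times ULN | Not needed |
| Syncope, presyncope, rash | None | None |

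The sentence in 14.2 that announces the laboratory counts cites Tables 3 and 4. The chemistry criteria are in Table 2, and I read it so.

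After baseline, Table S-1 schedules vital signs only at Weeks 1, 2 and 4, and at unscheduled visits. A faint or symptomatic fall in pressure at home therefore reaches the analysis as an adverse event term, if at all.

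**4. Where a QT adverse event would go.** It is absent from the events-of-interest table but enters the all-TEAE tables by body system and term, by severity, by relationship and by term alone. In an arm of 20 one event is 1/20 = 5%, which also meets the cut-off for the most-frequent-events table; in an arm of 21 it is 4.8% and does not.

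**The case against.** The strongest reply is that the watched findings are counted elsewhere. A reader might infer from the events-of-interest list that no table counts subjects with the reactions the protocol monitors. The documents do not support that: all three cardiovascular findings in Protocol 4.5.1.2 have a summary in SAP 14.3 or 14.4 with the protocol's own definitions, and ALT, AST, bilirubin and CK are covered in 14.2 (CK without the protocol's one-week duration). Nor would a QT adverse event be lost, as step 4 shows.

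Four further points are fair.

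- The word separately in SAP 14.1 most naturally means a separate table, since the same phrasing is used for fatal events. It should not be read as an instruction to keep terms apart.
- SAP 1 places table specifications in another document, which may contain grouped rows. What can be said is that the SAP text does not specify them.
- Nothing requires the list to mirror the stopping criteria. It already includes rash and syncope, which are not named criteria, and leaves out acute renal insufficiency, cardiopulmonary arrest and immediate drug reaction, which Protocol 4.5.1.3 names.
- With 61 subjects and by-subject listings, a reader can reconstruct the counts by hand. The repeated entries are editorial and change no count.

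These points limit the weight of the matter but do not remove it. The measured-value tables work per analyte or per visit measurement, the general TEAE tables have the same term-by-term structure, body system is not the same as reaction, and a count made by hand from a listing is not a planned summary.

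**Conclusion.** The point holds in a limited form. As the SAP text stands, the events-of-interest table gives no once-per-subject count across related terms and has no QT term. No other specified table supplies a combined hepatic or hypotension/syncope subject count, and syncope and rash have no measured-value counterpart.

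The size is the ambiguity shown above: with one subject in each row, 5% to 25% of an arm for hypotension/syncope and 5% to 35% for hepatic terms. This rests on equal allocation of 61 subjects and on an illustrative pattern of one event per term. It is a range of what the table could conceal, not a prediction.

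This is a low-cost improvement to a descriptive table in a terminated trial. It affects no efficacy conclusion and does not mean that QT or the other monitored findings go unsummarized.

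**What to change.** In SAP 14.1, add grouped rows to the events-of-interest table:

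- hepatic (the seven liver terms)
- CK increased
- rash
- hypotension/syncope (the five distinct terms)
- bradycardia
- QT prolongation (term added to the list)

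For each group report the number and percentage of subjects with at least one event, counting each subject once per group, by arm and for the two ACP-044 arms combined. Keep the preferred terms as sub-rows and remove the repeated entries.

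Describe the groups as groupings of the SAP's own list plus QT. They should not be presented as matched to the stopping criteria: Protocol 4.5.1.1 places CK under the liver criteria, and the coverage differs in the other ways noted above. If treatment codes have already been released, label the rows as an added summary.

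The cost is a few lines of SAP text and a lookup table for programming; no new data are collected. The drawback is that a group mixes terms of different seriousness, such as a low blood pressure reading and a syncope; the sub-rows keep that visible.

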14.2 Clinical Laboratory Variables

Clinical laboratory tests are performed at Baseline and Week 4 (EOT/ET).

The laboratory evaluations will include, but are not limited to, the following:

- Clinical chemistry serum tests (CHEM)
 - Sodium (Na), potassium (K), chloride (Cl), phosphorus (P), calcium (Ca), carbon dioxide (CO₂), blood urea nitrogen (BUN), creatinine (CR), uric acid,
 - Estimated glomerular filtration rate (eGFR) should only be performed at Visit 1 (Screening)

- Alanine aminotransferase (ALT), aspartate aminotransferase (AST), gamma-glutamyl transpeptidase (GGT), alkaline phosphatase (ALP), total bilirubin (TBIL), lactate dehydrogenase (LDH)
 - INR to be evaluated, as needed
- Creatine kinase (CK)/creatine phosphokinase (CPK)
- Lipid panel should only be performed at Visit 1 (Screening):
 - Total cholesterol, HDL-cholesterol, triglycerides, LDL-cholesterol, cholesterol/HDL ratio, non-HDL cholesterol; should only be performed at Visit 1 (Screening)
- HbA1c should only be performed at Visit 1 (Screening)
- Glucose
- Albumin (ALB) should only be performed at Visit 1 (Screening)
- Total protein should only be performed at Visit 1 (Screening)
- Hematology tests
 - Complete blood count (CBC) including:
 - White blood cell (WBC) count
 - Complete differential (relative and absolute)
 - Hematocrit (Hct), hemoglobin, red blood cells (RBC), platelets
 - Reticulocyte count
- Endocrinology
 - Thyroid stimulating hormone (TSH) and free T4 (Screening)
- Pregnancy test
 - A serum pregnancy test should only be performed at screening for women of childbearing potential
 - A urine pregnancy test should be performed at Baseline (Week 0) and Week 4 (EOT)/ET for women of child-bearing potential
 - If urine cannot be obtained in women of childbearing potential, a serum pregnancy test should be done in its place
- COVID-19 test:

- COVID-19 diagnostic PCR test at Screening
- Urinalysis (UA)
 - Blood, RBCs, WBCs, protein, glucose, ketones, specific gravity, pH, nitrates
- Urine drug screen (UDS) with reflex testing
 - A urine drug screen will test for controlled substances at Screening, Baseline Pain Assessment Period, and at Week 4/EOT/ET. A dipstick urine drug screen will be performed at Baseline (Week 0) for rapid detection of controlled substances and for certain prescription medications in order to determine if the subject continues to meet subject eligibility. The following controlled substances will be tested for with a urine drug screen and/or urine dipstick according to the schedule presented in Table 6–1 in protocol: amphetamine, barbiturates, benzodiazepines, buprenorphine, cocaine, ecstasy (MDMA), methadone, morphine/opiates, methamphetamine, marijuana (THC), phencyclidine (PCP), propoxyphene, tricyclic antidepressants. Negative drug screens are required for study eligibility.
 - If there is a positive urine drug screen for an analgesic medication that is not allowed per protocol, the subject must washout of medication, if appropriate, prior to the Baseline Pain Assessment Period.
 - If there is a positive urine drug screen for a medication that is allowed per protocol (e.g., metformin leading to a false positive for amphetamine), the subject must have a valid prescription for such medication, and if the subject denies use of the positive prohibited medication (e.g., amphetamine), they can be included in the study and it will not be considered a protocol deviation.

Clinical laboratory values (in Système International [SI] units) and the change from Baseline values will be summarized by treatment group at each post-Baseline visit using descriptive statistics. The overall minimum, maximum as well as the last post-Baseline observed and change from Baseline values will also be summarized. For urinalysis with categorical results, the number and percentage of subjects will be tabulated by category at Baseline and each post-Baseline visit, and the denominator is the number of subjects with non-missing values for the given parameter, visit and treatment group.

Laboratory values will also be summarized in shift tables by treatment group, to determine the number and percentage of subjects with values classified as below, within, and above normal ranges at each post-Baseline visit relative to the same classification at the Baseline

visit. For the by-visit shift summary, the denominator is the number of subjects with non-missing values at Baseline and the given visit for the given parameter and treatment group. For the shift to the overall post-Baseline minimum or maximum, all post-Baseline values will be considered, including unscheduled and out of window values and the denominator is the number of subjects with non-missing Baseline value and at least 1 post-Baseline value for the given parameter and treatment group.

Clinical laboratory values are potentially clinically important (PCI) if they meet either the low or high PCI criteria listed in Table 2 and Table 3. The number and percentage of subjects with post-Baseline PCI values for each of the categories in Table 3 and Table 4 will be summarized by treatment group for selected parameters. For the overall post-Baseline summaries of PCI values, all post-Baseline values will be considered, including unscheduled and out of window values. Subjects with multiple PCI values for a given parameter will be counted only once for that parameter. For the overall post-Baseline summary, the numerator of the percentage is the number of subjects with at least 1 post-Baseline PCI laboratory value for the given parameter and treatment group, and the denominator is the number of subjects with at least 1 post-Baseline laboratory value for the given parameter and treatment group.

Table 2 Criteria for Potentially Clinically Important Laboratory Values – Hematology and Chemistry

Analyte	Conventional Unit	Low PCI Criteria	High PCI Criteria	SI Unit	Low PCI Criteria	High PCI Criteria
Hematology (whole blood)						
Hemoglobin (male)	g/dL	<11	>18	g/L	<110	>180
Hemoglobin (female)	g/dL	<10	>17	g/L	<100	>170
Hematocrit (male)	%	<30	>55	L/L	<0.3	>0.55
Hematocrit (female)	%	<30	>50	L/L	<0.3	>0.5
Leukocyte (White Blood Cell Count)	x 10 ³ /uL	≤2.8	≥15	x 10 ⁹ /L	≤2.8	≥15
Neutrophils	x 10 ³ /uL	≤1.5	No upper limit	x 10 ⁹ /L	≤1.5	No upper limit
Platelet Count	x 10 ³ /uL	≤75	≥700	10 ⁹ /L	≤75	≥700
Chemistry (serum or plasma)						
ALT (SGPT)	U/L	No lower limit	≥3 X ULN	U/L	No lower limit	≥3 X ULN
AST (SGOT)	U/L	No lower limit	≥3 X ULN	U/L	No lower limit	≥3 X ULN
Total Bilirubin	mg/dL	No lower limit	≥1.5 ULN	umol/L	No lower limit	≥1.5 ULN
BUN	mg/dL	No lower limit	≥30.0	mmol/L	No lower limit	≥10.71
Creatine Kinase (CK)	U/L	No lower limit	≥3 ULN	U/L	No lower limit	≥3 ULN

Table 2 Criteria for Potentially Clinically Important Laboratory Values – Hematology and Chemistry (Continued)

Analyte	Conventional Unit	Low PCI Criteria	High PCI Criteria	SI Unit	Low PCI Criteria	High PCI Criteria
Sodium	mEq/L	≤125	≥155	mmol/L	≤125	≥155
Potassium	mEq/L	≤3.0	≥5.5	mmol/L	≤3.0	≥5.5
Calcium, total	mg/dL	<8.0	>11.0	mmol/L	<2.0	>2.75
Lactate Dehydrogenase (LDH)	U/L	No lower limit	≥3 X ULN	U/L	No lower limit	≥3 X ULN
Alkaline Phosphatase	U/L	No lower limit	≥3 X ULN	U/L	No lower limit	≥3 X ULN
Uric acid (male)	mg/dL	No lower limit	≥10.5	umol/L	No lower limit	≥624.75
Uric acid (female)	mg/dL	No lower limit	≥8.5	umol/L	No lower limit	≥505.75
Albumin	g/dL	≤2.6	≥6.0	g/L	≤26	≥60
Total Protein	g/dL	≤5.0	≥10.0	g/L	≤50	≥100
Chloride	mEq/L	≤85	≥120	mmol/L	≤85	≥120
Glucose (random)	mg/dL	≤45.1	≥200.0	mmol/L	≤2.48	≥11
Serum Creatinine	mg/dL	Not Applicable	>1.5 ULN	umol/L	Not Applicable	>1.5 ULN
Triglycerides	mg/dL	Not Applicable	>300	mmol/L	Not Applicable	>3.39
Gamma-Glutamyl Transferase (GGT)	U/L	Not Applicable	≥3 ULN	U/L	Not Applicable	≥3 ULN

Table 3 Criteria for Potentially Clinically Important Laboratory Values - Urinalysis

Urinalysis (qualitative dipstick)	Low PCI Criteria	High PCI Criteria
Blood (occult blood)	Not Applicable	≥ Moderate
Protein	Not Applicable	≥ 100 mg/dL
Glucose	Not Applicable	≥ 500 mg/dL

Clinical laboratory data will be displayed in data listings with date and study day of collection. All units will be displayed according to SI conventions for units. Out of range values will be flagged in the data listings (i.e., ‘L’ or ‘H’). A separate listing will be provided for a subset of the chemistry, hematology, and urinalysis analytes with values classified as PCI.

The pregnancy results (positive or negative) for female subjects will be presented in a listing.

In addition, the following additional PCI criteria for liver function tests will be flagged, listed, and summarized:

- ALT (SGPT) ≥ 2x ULN U/L

- AST (SGOT) $\geq 2x$ ULN U/L
- Gamma Glutamyl Transferase $\geq 2x$ ULN U/L
- Alkaline Phosphatase $\geq 2x$ ULN IU/L
- Creatine Kinase (CK) $\geq 5x$ ULN

